3.4 Study Groups

This study is a randomized, double-blinded placebo controlled single center clinical trial conducted at OSU Wexner Medical Center of 110 women with diagnosis of preeclampsia with severe features. These women will be randomized at the time of admission to the labor & delivery unit to one of two groups:

- Daily Nifedipine 30mg XL
- Identical appearing placebo

Participants in the study will have the study medication administered by their nurse at time of enrollment and randomization, and every 24 hours thereafter until delivery. All other obstetric care will be at the discretion of the primary provider, including but not limited to: treatment of hypertensive urgency, timing and mode of delivery. Data will be collected on these components of routine obstetric care.

3.5 Population and Eligibility Criteria

a) Setting: This single center study will be conducted at The Ohio State University Wexner Medical Center.

b) Inclusion criteria:

1. Women aged 18-45 with a viable single or twin intrauterine pregnancy between 22 0/7 and 41 6/7 weeks gestation based on the best obstetric estimate by ACOG criteria.
2. Diagnosis of preeclampsia with severe features with decision made to induce labor. The patient may or may not have already received acute treatment for severe blood pressures.

c) Exclusion criteria:

- Known allergy or adverse reaction to Nifedipine or any medical condition where Nifedipine is contraindicated, such as galactose intolerance, severe GI stricture, and GI hypomotility disorder.
- Currently receiving Nifedipine XL as part of hypertension management prior to induction of labor
- Participation in another trial that affects the primary outcome without prior approval
- Physician/provider or patient refusal

- Participation in this trial in a prior pregnancy
- Triplet or higher order pregnancy

3.6 Gestational Age Determination

Gestational age is determined using criteria proposed by the American Congress of Obstetricians and Gynecologists, the American Institute of Ultrasound in Medicine, and the Society for Maternal-Fetal Medicine, and is denoted “project gestational age.” The “project EDC,” which is based on the project gestational age, cannot be revised once a determination has been made. If the pregnancy is conceived by in-vitro fertilization, project gestational age is calculated from the date of embryo transfer and the embryo age at transfer. If the pregnancy is conceived spontaneously (including ovulation induction and artificial insemination) information from the earliest dating ultrasound and the last menstrual period are used to determine project gestational age. If no dating ultrasound has been performed previously, one must be performed before the patient can be randomized.

The following algorithm is used:

- The first day of the last menstrual period (LMP) is determined, and a judgment made as to whether or not the patient has a “sure” LMP date.
- If the LMP date is unsure, ultrasound measurement(s) obtained at the patient’s first dating ultrasound examination is used to determine the project gestational age. If the first dating ultrasound was conducted before 14 weeks 0 days, the measurement must be based on crown rump length (CRL).
- If the LMP date is sure, project gestational age is determined by a comparison between the ultrasound measurements based on the earliest dating ultrasound. If the ultrasound confirms the gestational age by LMP as in the table below, the LMP-derived gestational age is used to determine the project gestational age. Otherwise, project gestational age will be determined based upon the ultrasound measurement.

Table 1. Cutoffs for using LMP to determine gestational age for sure LMP

Gestational age at first ultrasound by LMP	Ultrasound agreement with LMP
up to 8 6/7 weeks (by CRL)	≤5 days
9 0/7 weeks to 13 6/7 weeks (by CRL)	≤7 days
14 0/7 to 15 6/7 weeks	≤7 days
16 0/7 to 21 6/7 weeks	≤10 days

*CRL = Crown Rump Length

3.7 Randomization Method and Masking

Randomization may occur upon confirmation that all inclusion/exclusion criteria are satisfied, after verification of participant consent and HIPAA authorization.

Consenting women will be randomly assigned to nifedipine 30XL and placebo in a 1:1

ratio according to a randomization sequence prepared by and maintained by independent statistician and available from central investigational pharmacy who will dispense study drug or placebo. The two study arms are double masked; neither the patient nor the clinical staff will be aware of the treatment assignment.

The simple blocked randomization method will be used to generate the randomization sequences because it provides a high probability of balance in treatment assignments, it is unpredictable, and it allows an explicit randomization analysis to be conducted with relative ease.

4.0 Study Procedures

4.1 Screening and Eligibility and Consent

The participant's inclusion and exclusion criteria will be verified as will her interest in the study. The informed consent process will be conducted by trained research staff and will include all aspects of the study and a full disclosure of the risks, benefits, procedures, and alternatives. The study consent and HIPAA authorization will be signed after all questions have been discussed and answered. Collection of baseline information, including contact information, demographic and pregnancy history information, will follow the informed consent process.

4.2 Randomization and Baseline Visit Procedures

Randomization may occur upon confirmation that all inclusion/exclusion criteria are satisfied, after verification of participant consent and HIPAA authorization. Study staff will also verify participant contact information and obtain a Release of Information, as permitted by local policy, to collect outcome and serious adverse event (SAE) documentation. Patients will be assigned next sequential number and central pharmacy will dispense study drug or placebo depending on randomization allocation sequence.

Once the patient is randomized, the patient will receive a study drug or placebo from clinical nurse. She will be instructed to take 1 pill daily until delivery.

In addition to information collected for eligibility, gestational age, and EDC determination, the following information will be obtained at randomization from a patient interview followed by a review of her chart:

- Demographic information: age, race, insurance status
- Medical history: pre-pregnancy weight, current weight, height, chronic disease history
- Obstetrical history including outcomes of all prior pregnancies and which pregnancy(ies) was complicated by preeclampsia.
- Social history: marital status, years of education, alcohol use, tobacco use, and maternal drug use
- Record baseline blood pressure, and baseline preeclampsia laboratory data including platelets, creatinine, liver function tests and proteinuria status, if performed
- Medication use e.g. ASA prior to enrollment, antihypertensive medications including prior administration of acute antihypertensive medications, metformin, anti-platelet agents, etc

4.3 Obstetric Management

All aspects of obstetric management will be left to the patient's provider. Data will be collected on baseline laboratory values (when obtained), surveillance ultrasounds for fetal growth, antenatal testing, and timing and mode of delivery.

5.0 Sample Size and Power

For the purposes of sample size estimation, it is assumed that 85% of women with diagnosis of preeclampsia with severe features receive acute IV antihypertensive therapy and 74% will require additional IV hypertensive therapy throughout induction of labor process. Assuming rate of additional acute IV antihypertensive (primary outcome) without use of maintenance long acting antihypertensive therapy is 74%. It is estimated that sample size of 110 women is required to demonstrate at least a 40% reduction in use of additional acute antihypertensive therapy with the use of nifedipine 30XL (from 74% to 44%), with a power of 80%, and type I error of 5% 2-sided.

Primary Outcome		Treatment Effect	Power	Total N
Placebo	Nifedipine			
75%	52.5%	30% reduction	80%	140
			85%	160
			90%	188
	45%	40% reduction	80%	82
			85%	92
			90%	108
70%	49%	30% reduction	80%	170
			85%	194
			90%	226
	42%	40% reduction	80%	97
			85%	110
			90%	128
65%	45.5%	30% reduction	80%	202
			85%	230
			90%	270
	39%	40% reduction	80%	114
			85%	130
			90%	150

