2.6 Statistical Analysis Plan

Standard comparisons of characteristics between groups will be conducted at baseline. It

is anticipated that the randomization scheme will balance the groups for these covariates and they will not be adjusted for in the primary analysis.

The primary analysis will compare incidence of the outcome between the 2 study groups. If the two groups show a difference in the incidence of the primary outcome, interactions will be evaluated and subgroup analyses conducted to determine whether the effect prevails.

Lost to follow up should not occur given study design and no follow up is scheduled. Since many of the secondary endpoints are dichotomous variables like the primary outcome, standard statistical methods for rates and proportions will be appropriate. Continuous variables will be compared using standard statistical methods,

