6.0 Data Management

6.1 Data Collection Forms

Data will be collected on standardized forms on which nearly all responses have been pre-coded. Each form is briefly described below.

- Screening Log
- Eligibility Checklist
- Randomization: completed for all eligible women, lists randomized drug code number
- Baseline Form: includes detailed demographic and social data, medical & obstetrical history, and current pregnancy complications (to date), as applicable
- Study Drug lots: documents dispensing of study medication and the return of any unused study medication
- Maternal delivery and outcome forms: documents labor, delivery and postpartum information through the first 7 days after delivery
- Neonatal baseline form: records date and time of birth, delivery data and status at delivery for each fetus/infant
- Neonatal outcome form: records outcome data for all infants admitted to the NICU or special care nursery
- Patient status form: documents loss to follow-up/withdrawal status, side effects since the last dose
- Will do an intrapartum BP log.

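### Section 5.0 says 110 women are required for 80% power (74% vs 44%), but 82 to 96 suffice depending on the test, and 110 give about 86% to 90%

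*Combined protocol and SAP*

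**What the plan says.** Section 5.0 (Sample Size and Power) takes 74% as the placebo rate of additional acute antihypertensive therapy, the primary outcome. It then justifies N: "It is estimated that sample size of 110 women is required to demonstrate at least a 40% reduction in use of additional acute antihypertensive" treatment. The rate on nifedipine is put at 44%, and the design is specified "with a power of 80%, and type I error of 5% 2-sided". Section 3.7 gives 1:1 allocation, so 110 means 55 per arm.

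The table under that sentence lists total N for placebo rates of 75%, 70% and 65%, for relative reductions of 30% and 40%, and for power of 80%, 85% and 90%. It has no 74% row.

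The analysis section (headed 2.6) names no test for the primary outcome: "The primary analysis will compare incidence of the outcome between the 2 study groups". On attrition it says: "Lost to follow up should not occur given study design and no follow up is scheduled". Section 6.1 does list a form that records withdrawal ("Patient status form: documents loss to follow-up/withdrawal status, side effects since the last dose"), but no withdrawal rate or inflation of N appears anywhere.

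**The concern.** The table row closest to the sentence is 75% vs 45%, with the same 30-point difference. It gives 82 women for 80% power and 108 for 90%. Moving both rates down by one point cannot raise 82 to 110. The only 110 in the table belongs to 70% vs 42% at 85% power, which matches neither the placebo rate nor the power in the sentence.

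This sentence is the plan's justification for its sample size. If it is wrong, the stated power is wrong, and the plan gives no reason for enrolling more women than its stated target needs. If the result is null, a reader relying on the stated 80% would underrate what the trial could have detected.

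**Working it through.** **Inputs.** Placebo 74%, nifedipine 44%, power 80%, two-sided 5% (section 5.0); 1:1 allocation (section 3.7); no inflation stated. A 40% reduction from 74% is 0.60 × 74% = 44.4%, so both 44% and 44.4% are tried.

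**Step 1: identify the table's method.** Pooled-variance formula, per arm, with p̄ = (p1 + p2)/2:

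n = [1.960·√(2p̄(1−p̄)) + z_power·√(p1(1−p1) + p2(1−p2))]² / (p1 − p2)²

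Rounded up per arm and doubled:

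| Rates | Table (80/85/90%) | Formula (80/85/90%) |
|---|---|---|
| 75% vs 52.5% | 140 / 160 / 188 | 142 / 162 / 188 |
| 75% vs 45% | 82 / 92 / 108 | 82 / 94 / 108 |
| 70% vs 49% | 170 / 194 / 226 | 170 / 194 / 226 |
| 70% vs 42% | 97 / 110 / 128 | 98 / 110 / 128 |
| 65% vs 45.5% | 202 / 230 / 270 | 202 / 232 / 270 |
| 65% vs 39% | 114 / 130 / 150 | 114 / 130 / 152 |

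Twelve of the 18 entries agree exactly and the other six within 2 patients, so the table evidently comes from this formula or one very close to it.

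**Step 2: apply it to the sentence.** For 74% vs 44%, p̄ = 0.59.

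- First term: 1.960 × √(2 × 0.59 × 0.41) = 1.3633.
- Second term at 80% power: 0.8416 × √(0.74 × 0.26 + 0.44 × 0.56) = 0.5575.
- n = (1.3633 + 0.5575)² / 0.30² = 41.0, so 41 per arm, **82 in total**.

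The same formula gives 94 at 85% power and 110 at 90%.

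**Step 3: other methods at 80% power.**

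| Method | 74% vs 44% | 74% vs 44.4% |
|---|---|---|
| Pooled | 82 | 86 |
| Arcsine | 82 | 84 |
| Unpooled | 78 | 80 |
| Continuity-corrected | 96 | 98 |
| Fisher, exact power | 96 | 98 |

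For 74% vs 44%, exact Fisher power is 79.5% at 94 women and 80.6% at 96. A one-sided pooled calculation gives 66. No method gives 110 at 80% power.

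**Step 4: power with 55 per arm, by enumerating all outcomes.**

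| Test | 74% vs 44% | 74% vs 44.4% |
|---|---|---|
| Uncorrected chi-square | 90.2% | 89.4% |
| Fisher's exact | 85.9% | 85.0% |

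The pooled formula gives 90.3% for 74% vs 44%.

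**Step 5: effect that 110 women detect at 80% power.** With a 74% placebo rate the detectable nifedipine rate is about 48.2% uncorrected, a relative reduction of (74 − 48.2)/74 = 35%. With Fisher's test it is about 46.3%, a reduction of (74 − 46.3)/74 = 37%.

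**Step 6: could attrition explain 110?** It would take 1 − 82/110 = 25.5% loss from 82, or 1 − 96/110 = 12.7% from 96. The plan states neither.

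**The case against.** The strongest reply is that little follows from this. The trial is larger than its stated target needs, the effect and the type I error are explicit, and a reader who looks at the 75% vs 45% row can see that 110 women give close to 90% power. That is fair: only the power figure, the test and the reason for 110 are in doubt, and no patient or analysis is affected.

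There are also innocent explanations. The pooled formula gives exactly 110 at 90% power for 74% vs 44%, so 80% may be a slip for 90%. Alternatively, 110 may be a margin against a lower placebo rate: by the plan's own table it covers a 40% reduction at 80% power from 75% (82) or 70% (97), and falls just short from 65% (114). Either is plausible, but the documents support neither over the other, and on either reading the sentence misdescribes the design.

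The range also depends on rounding. With 44.4% in place of 44%, the required N is 86 to 98 and the surplus is 12 to 24 women. The unpooled formula, which does not match the table, goes as low as 78. None of this closes the gap to 110.

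**Conclusion.** The concern holds. For the stated 74% vs 44%, two-sided 5% and 1:1 allocation, 80% power needs 82 women (uncorrected) to 96 (continuity-corrected or Fisher), not 110. With 110 women the power is about 86% to 90%, so the sentence understates it by about 6 to 10 percentage points and asks for 14 to 28 more women than its target requires. With 44.4% the lower end of the power range is 85%. These figures assume that all 110 women contribute to the primary analysis, as the plan expects, and that the placebo rate is 74%. The error is in the safe direction. It is a misstatement of the sample size justification that should be corrected, not a threat to the trial's validity.

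**What to change.** Rewrite the sample size sentence in section 5.0 so that N, power, effect and test agree, and name the same test in the analysis section. One possible wording: 110 women (55 per arm) give about 90% power with an uncorrected chi-square test (about 86% with Fisher's exact test) to detect 74% vs 44% at two-sided 5%, or 80% power to detect 74% vs about 48% with the uncorrected test. Give only the figure for the test chosen.

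If 110 includes an allowance for withdrawal, or a margin for a lower placebo rate, state its size, the reason and the N before it was added. The cost is one or two sentences; no extra patients and no change in N are needed.

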2.6 Statistical Analysis Plan

Standard comparisons of characteristics between groups will be conducted at baseline. It

is anticipated that the randomization scheme will balance the groups for these covariates and they will not be adjusted for in the primary analysis.

The primary analysis will compare incidence of the outcome between the 2 study groups. If the two groups show a difference in the incidence of the primary outcome, interactions will be evaluated and subgroup analyses conducted to determine whether the effect prevails.

Lost to follow up should not occur given study design and no follow up is scheduled. Since many of the secondary endpoints are dichotomous variables like the primary outcome, standard statistical methods for rates and proportions will be appropriate. Continuous variables will be compared using standard statistical methods,

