2.0 Background

Preeclampsia complicates approximately 1 in 25 pregnancies², and is therefore a relatively common obstetric complication. It is the second leading cause of maternal mortality worldwide after hemorrhage, and may lead to maternal comorbidities including stroke, eclampsia, and organ failure. Fetal or neonatal outcomes include intrauterine growth restriction, low birth weight, and stillbirth. Many of the complications associated with preeclampsia lead to early induction of labor or cesarean delivery and subsequent preterm birth.

Preeclampsia with severe features may be diagnosed in the absence of severe blood pressures, defined as systolic blood pressure (SBP) ≥ 160 mm Hg or diastolic blood pressure (DBP) ≥ 110 mm Hg, when other severely defining features are present. These include clinical features (persistent headache or vision disturbances), laboratory features (liver enzymes twice the upper limit of normal, thrombocytopenia with platelet count less than 100,000/mL, or creatinine greater than 1.1mg/dL, or end organ injury). When severe blood pressures are present, prompt management is required to avoid sequelae such as stroke or placental abruption. Existing data support the use of oral Nifedipine or intravenous hydralazine or labetalol for the treatment of hypertensive urgency in pregnancy¹. Optimal treatment for severe blood pressure during induction of labor for the diagnosis of preeclampsia with severe features has not been described, but inadequate blood pressure control is a risk factor for cesarean

delivery. In a review of the Consortium for Safe Labor, at least 27% of women undergoing induction of labor for preeclampsia with severe features between 24-34 weeks gestation required a cesarean delivery for hypertensive disease³. In a review of over 200,000 women using the Prospective database, the frequency of any antihypertensive use in preeclampsia increased between 2006 and 2014, with corresponding risk reduction in stroke⁴.

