3.0 Study Design

This is a randomized double blind placebo controlled trial comparing Nifedipine 30mg XL to placebo in 110 patients after decision has been made to proceed with induction of labor for the diagnosis of preeclampsia with severe features.

Potential study participants will be identified at the time of admission to the labor & delivery unit. Eligibility criteria will be verified. At the time of enrollment, patients will be randomized to either the study drug (oral Nifedipine XL 30mg) or identical placebo. Participants will receive the first dose of the study medication after enrollment unless recorded blood pressure is <120/70. Dosing will continue every 24 hours through delivery. Algorithms for the administration of intravenous labetalol or hydralazine will be utilized by the primary provider at his or her discretion. Postpartum management of hypertension with oral medications will be unblinded and at the provider's discretion.

This study is a randomized, double-blind, placebo controlled single center clinical trial conducted at The Ohio State University Wexner Medical Center, where approximately 216 women are delivered for preeclampsia with severe features each year. These women will be randomized at the time of induction of labor into two groups.

- Oral administration of 30mg Nifedipine XL q24 hours until delivery
- Matching placebo group q24hrs until delivery
- Women may take the study drug/placebo concurrently with intravenous labetalol or hydralazine or immediate release Nifedipine for the treatment of severe blood pressures during cervical ripening and/or induction of labor per unit protocol.
- All other obstetric care will be at the discretion of the primary provider, including but not limited to cervical ripening and augmentation methods, intrapartum resuscitation, IV magnesium for seizure prophylaxis and recommendations regarding mode of delivery. Data will be collected on these components of routine obstetric care. Analysis will be by intent to treat.

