3.1 Preeclampsia with severe features diagnosis determination

Among women without a history of chronic hypertension, preeclampsia without severe features is typically made based on elevated blood pressures and proteinuria greater than 300mg/24 urine collection; however, in the absence of proteinuria, the severely-defining features below can be used for diagnostic purposes. Preeclampsia with severe features is diagnosed based on the following:

- Development of hypertension, defined as a persistent SBP of 160mm Hg or higher, or DBP of 110mm Hg or higher on two occasions at least 4 hours apart while the patient is on bedrest (unless antihypertensive therapy is initiated before this time)
- Alternatively, the diagnosis can be made with a SBP of 140 mm Hg or higher, or a DBP of 90 mm Hg or higher after 20 weeks of gestation in a patient with previously normal blood pressure, plus any of the following:
 - Thrombocytopenia, with platelet count of less than 100,000/microliter
 - Impaired liver function as indicated by abnormally elevated blood concentrations of liver enzymes (to twice normal concentration), severe persistent right upper quadrant or epigastric pain unresponsive to medication and not accounted for by alternative diagnoses, or both
 - Progressive renal insufficiency (serum creatinine concentration greater than 1.1mg/dL or a doubling of the serum creatinine concentration in the absence of other renal disease
 - Pulmonary edema
 - New-onset cerebral or visual disturbances

- In women with baseline chronic hypertension, preeclampsia is diagnosed based on any of the following (not accounted for by alternative diagnoses):
 - Severe hypertension (SBP \geq 160 mmHg or DBP \geq 110 mmHg) \geq 20 weeks in gestation on two occasions with measurements taken at least 4 hours apart or 1 occasion with subsequent antihypertensive therapy, or an escalation of antihypertensive medications to control blood pressure
 - New onset of proteinuria or a doubling in protein in women with baseline proteinuria
 - Thrombocytopenia (platelet count $<$ 100,000 per microliter)
 - Progressive renal insufficiency (serum creatinine $>$ 1.1 mg/dl or doubling of the serum creatinine in the absence of other renal disease)
 - Impaired liver function (elevated transaminases \geq 70 U/L, or severe persistent right upper quadrant or epigastric pain unresponsive to medication)
 - Pulmonary edema diagnosed clinically by exam or chest x-ray

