3.2 Study Aims

The primary aim is the need for intravenous or immediate-release oral therapy for acute treatment of severe hypertension.

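### Expected balance does not justify leaving baseline blood pressure and prior acute treatment out of the primary analysis; adjusting is a cheap, conditional gain in precision, not the correction of an error

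*Combined protocol and SAP*

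**What the plan says.** Section 2.6 (Statistical Analysis Plan) plans baseline comparisons between the arms, expects randomization to balance the covariates, and states that "they will not be adjusted for in the primary analysis". It gives no other reason. The primary analysis is a comparison of incidence between two groups; no test or effect measure is named and no adjusted supporting analysis is described, though none is ruled out.

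Section 3.7 describes 1:1 allocation: "The simple blocked randomization method will be used to generate the randomization sequences". No stratification factor is named.

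The outcome in section 3.2 is the "need for intravenous or immediate-release oral therapy for acute treatment of severe hypertension". Women can enter with quite different pressures:

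- Section 2.0 notes that "Preeclampsia with severe features may be diagnosed in the absence of severe blood pressures".
- Section 3.1 sets out a route by which "the diagnosis can be made with a SBP of 140 mm Hg or higher", given other features, as well as a route from 160 mm Hg.
- Section 3.0 provides for a low reading at entry: participants get the "first dose of the study medication after enrollment unless recorded blood pressure is <120/70".
- Section 3.5 admits women whether or not they have already had acute treatment.

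Section 4.2 collects both variables at randomization: baseline blood pressure, and medication use that covers "antihypertensive medications including prior administration of acute antihypertensive medications".

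**The concern.** Two questions are run together in section 2.6. Randomization, with or without observed balance, makes the unadjusted test valid. Precision is separate: a covariate that predicts the outcome reduces the variance of the treatment contrast even when the arms are perfectly balanced on it. The stated reason therefore does not address what would be lost by leaving the covariates out.

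The outcome is acute treatment of severe hypertension, so pressure at entry and earlier acute treatment are natural candidates for prognostic covariates. The absence of stratification does not oblige adjustment; it only means that no design feature already uses these variables. What is at stake is some power and a narrower interval at no recruitment cost, chiefly if the true effect is smaller than planned. The choice is credible only if fixed in advance, because an adjusted analysis added after unblinding would be post hoc.

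**Working it through.** **1. The plan's own power.** Inputs from section 5.0: control rate 74%, nifedipine rate 44%, two-sided 5%, 110 women (55 per arm). With pooled variance, power = Φ[(d − 1.96·√(2p̄q̄/n)) / √((p₁q₁ + p₂q₂)/n)].

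- 74% vs 44%: d = 0.30, p̄ = 0.59. Pooled SE = √(0.4838/55) = 0.0938; unpooled SE = √(0.4388/55) = 0.0893. (0.30 − 0.1838)/0.0893 = 1.30, power 90.3%. Fisher's exact test gives 85.9%.
- The stated 110 at 80% power is not reproduced: this formula needs 82 (96 with continuity correction), and 110 is its 90% figure. The discrepancy errs towards more power and is separate from this point.
- 30% reduction: 0.74 × 0.70 = 51.8%. d = 0.222, p̄ = 0.629. (0.222 − 0.1806)/0.0897 = 0.46, power 67.8%. Section 5.0 tabulates 30% reductions from 75%, 70% and 65%, but the trial is not sized for them.

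**2. Rough size of a gain.** If covariates explain a share R² of outcome variance, effective n per arm is about 55/(1 − R²). For R² = 0.05, 0.10, 0.20, 0.30 this is 57.9, 61.1, 68.8, 78.6. Power at 74% vs 51.8% becomes 70.1%, 72.5%, 77.5%, 82.8%; at 74% vs 44% it becomes 91.7%, 93.1%, 95.5%, 97.5%. At R² = 0 there is no gain.

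**3. Simulation of a specific analysis.** The estimator is logistic regression on treatment, SBP and prior treatment, standardized to a risk difference. Its influence-function variance is multiplied by n/(n − p) (110/106 = 1.038 with p = 4) and referred to t on n − p df. Prior treatment is dropped if the fit fails. The comparator is the chi-square test.

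Assumed, because the documents give no figures:

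- Odds ratios per SD of SBP and for prior treatment, as in the table.
- Correlation between the two covariates of −0.5, −0.3, 0 and +0.3.
- 85% treated before randomization, with 50% as a check. Section 5.0 assumes that "85% of women with diagnosis of preeclampsia with severe features receive acute IV antihypertensive therapy" but does not say that this is before randomization.

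The variance ratio is unadjusted over adjusted; ranges run over the correlations. Power columns use 85% treated and are in percent.

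| OR per SD SBP / OR prior treatment | Variance ratio, 85% treated | Variance ratio, 50% treated | Adjusted power, 74 vs 52 | Same, test held to exactly 5% | Adjusted power, 74 vs 44 |
|---|---|---|---|---|---|
| 1 / 1 | 0.98 | 0.98 | 68 | 67-68 | 90 |
| 1.2 / 1.5 | 0.98-1.00 | 0.99-1.01 | 68-69 | 67-69 | 90-91 |
| 1.5 / 3 | 1.01-1.07 | 1.03-1.11 | 69-73 | 69-72 | 91-92 |
| 2 / 4 | 1.05-1.18 | 1.07-1.23 | 72-75 | 71-74 | 92-94 |
| 2.5 / 5 | 1.09-1.27 | 1.12-1.31 | 73-79 | 72-78 | 93-96 |

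Unadjusted power in the same runs was 68-70% and about 90%. Where the covariates are prognostic, the gain is smallest at correlation −0.5 (prior treatment may already have lowered the recorded pressure) and largest at +0.3. With the test held to 5% (correlations −0.5, 0 and +0.3), the change in power at 74% vs 52% is −2 to 0 points in the first two rows, then 0 to +2, +2 to +5 and +3 to +9.

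Mean 95% interval width at 74% vs 44% is 0.347 unadjusted. Adjusted, it is 0.354 in the first row and 0.315-0.334 in the last.

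**4. Error rate and stability.** Rejection under the null was 4.7-5.1% unadjusted, 5.1-5.5% adjusted with the small-sample correction, and 5.8-6.3% without it. The fit failed in 0-2.1% of trials; at 85% treated, only 55 × 0.15 ≈ 8 untreated women per arm are expected. Monte Carlo error on the null rates is about 0.13 points.

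**5. Cross-check.** A separate simulation (3,000 trials per setting, independent covariates, normal reference) gave, at 74% vs 51.8%, 69.2% adjusted vs 69.3% unadjusted at R² = 0, and 80.3% vs 70.4% at R² of about 0.24.

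**The case against.** The unadjusted comparison of two proportions is pre-specified, transparent and valid, and at the design effect it has about 90% power against the 80% asked for. No gain is demonstrated for this trial, since prognostic strength, correlation and the share treated before entry are all assumed. If earlier treatment has already lowered the recorded pressure, the variance ratio is only 1.01 (1.5/3) or 1.05 (2/4). The 68-79% range is not level-matched and belongs to an effect the trial was not sized for. The adjusted test is slightly liberal and the fitted model can depend on the data. A pre-specified adjusted sensitivity analysis would avoid both problems.

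All of this is right as fact, and it is why the point is an improvement and not a defect. It does not supply the missing argument in section 2.6: expected balance still says nothing about precision, and the likely loss is about 2% of variance against a possible gain several times larger.

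A sharper objection concerns the outcome. Section 3.2 speaks of any acute therapy, whereas sections 1.3 and 5.0 speak of additional therapy. If additional meant beyond a treatment already given before randomization, prior treatment would be partly built into the outcome and the model could fail to fit. The documents do not state that reading. Under it, the fallback to SBP alone would apply, and SBP alone still gave a variance ratio of about 1.07 at 2/4. The outcome wording should nevertheless be settled before this covariate enters the primary model.

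**Conclusion.** The point holds as a worthwhile, low-cost change; leaving the plan as it stands would not invalidate the trial. The only reason given for excluding adjustment does not bear on precision, and both candidate covariates are already collected.

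The size of the benefit is conditional. It is nil, with up to about 2% of variance lost, if the covariates are weak. It is worth 2 to 9 percentage points of level-matched power at a 30% reduction if odds ratios are around 2/4 to 2.5/5, and little at the planned 74% vs 44%. These figures rest on the assumed odds ratios, correlations and proportion previously treated, none of which the documents supply. Confidence that the change would help this particular trial is therefore moderate.

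**What to change.** Before unblinding, and after settling whether the outcome is any or additional acute therapy, replace the sentence in section 2.6 with wording such as:

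> The primary analysis estimates the risk difference (and risk ratio) by logistic regression on treatment, baseline SBP (continuous; the baseline reading recorded at randomization) and acute antihypertensive treatment before randomization (yes/no), standardized over all randomized women. The robust variance is multiplied by n/(n − p) and referred to a t distribution with n − p degrees of freedom, p being the number of parameters in the fitted model. Missing baseline SBP is replaced by the overall mean and missing prior treatment by the most frequent category, both pooled over arms. If the model does not converge, prior treatment is dropped. The unadjusted comparison of incidence is reported alongside.

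Standardizing keeps the target a marginal comparison of incidence; an adjusted odds ratio would be a different quantity. Using SBP alone is a parsimony choice, since section 2.0 defines severe pressure by either component. Adding DBP (p = 5; assumed correlation 0.6 with SBP and no added prognostic value) lowers the variance ratio from 0.98, 1.05 and 1.13 to 0.97, 1.04 and 1.11 at 1/1, 1.5/3 and 2/4 with correlation 0.

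The cost is SAP wording and a little code, with no new data. The price is a model-based primary result, a slightly liberal test (5.1-5.5% here; allow 5.0-5.8% across simulation set-ups) and a convergence rule that lets the fitted model depend on the data. With 5% of each covariate missing and the rule above, the variance ratio at 2/4 is 1.04-1.17 instead of 1.05-1.18, and null rejection is 5.2-5.4%. If the sponsor prefers to keep the unadjusted comparison primary, the same model should be pre-specified as a supporting analysis; that gives up the gain in the primary test.
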